8.9 Clinical Safety Laboratory Evaluations

8.9.1 Standard safety laboratory tests

Laboratory results obtained in the course of standard medical care should be used to provide the information required below whenever available. All these tests are required at screening/baseline, Day 4, 7, 14, 21 and 28, except pregnancy testing (screening/baseline only)

All the following tests will be performed by the local laboratory.

- Chemistry:
 - Miscellaneous: glucose, osmolality, bicarbonate, total protein, albumin
 - Electrolytes: sodium, potassium, chloride, calcium
 - Liver function: total bilirubin, alanine transaminase (ALT), aspartate transaminase (AST), lactate dehydrogenase (LDH), alkaline phosphatase
 - Miscellaneous enzymes: creatine kinase (CK), amylase, C-reactive protein (CRP)
 - Renal function: blood urea nitrogen, creatinine, serum eGFR, phosphorus
- Hematology & coagulation
 - Red blood cell (RBC), hemoglobin, hematocrit
 - WBC, neutrophils, lymphocytes, basophils, eosinophils, and monocytes (absolute counts or %)
 - INR, fibrinogen, platelets
- Urine: glucose, protein, RBC, WBC
- Pregnancy test for women of childbearing potential (serum or urine, screening only)

8.9.2 Immunogenicity (ADA)

- The corresponding sample will be collected, stored and shipped per instructions (see laboratory manual).
- Samples will be obtained at screening/baseline and Day 28.
- Assays will be performed by a central laboratory.

- A primary and a back-up sample of 1.5 mL each of serum will be collected and stored at -20° C.

8.9.3 Future biomarker samples will be collected, where applicable.

- The corresponding sample will be collected, stored and shipped per instructions (see laboratory manual).
- Samples will be obtained at Day 4, 7, 14, 21, and 28.
- Assays will be performed at a central laboratory.

8.10 Vital Signs

Vital signs include heart rate, arterial blood pressure, respiratory rate, and temperature.

Maximum daily temperature (defined as the maximum temperature reported on a single calendar day) will be recorded. Body temperature may be taken per the site's preferred method but limited to oral, tympanic, rectal or core measurements and will be recorded in the appropriate eCRF. The same method of measuring a patient's body temperature should be used throughout the study.

8.10.1 Baseline, Treatment, and Daily in-ICU

Vital signs will be recorded at baseline prior to treatment (time 0), and then at 1, 2, 4, 12 and 24 hours post treatment. Vital signs will also be recorded daily thereafter.

8.11 Electrocardiograms

A standard 12-lead ECG will be obtained at baseline for reference. Abnormal ECG finding that would be observed during the course of the study will be duly documented and if appropriate, reported as adverse events.

8.12 Physical Examinations

A standard physical exam by body systems (General Appearance, Head and Neck, Lymph Nodes, Cardiac, Pulmonary, Abdominal, Genitourinary, Osteoarticular, Extremities, Cutaneous, Neurological) will be performed at baseline, then at Day 4, 7, 14, 21, and 28 or in case of early termination. Changes from baseline will be assessed and if appropriate, reported as adverse events.

8.13 Chest X-rays

Minimum of one Chest X-rays or a sequence of at least 2 Chest X-rays showing the presence of new or progressive infiltrate(s) suggestive of bacterial pneumonia to diagnose a pneumonia needs to be taken during screening. Chest X-rays may be taken at any time during the course of the study if medically necessary. All clinically relevant Chest X-rays may be uploaded to SureClinical.

8.14 Airway specimen

Airway specimens will be collected by only acceptable methods such as BAL, mini-BAL, or protected endotracheal tube aspiration or by sputum after extubation as outlined in the

microbiology laboratory manual. Additionally, please refer to the manual for detailed handling, storing and shipping procedures.

9 STATISTICS

9.1 Analytical Populations

9.1.1 Safety Population (Safety)

All subjects who have received the investigational therapy.

9.1.2 Modified Intent-to Treat Population (mITT)

All subjects who have been randomized and treated with any amount of study drug, regardless of microbiological documentation.

9.1.3 Microbiological Intent-to-Treat Population (micro-ITT)

All mITT subjects for whom microbiological documentation of pneumonia due to *P. aeruginosa* at screening / baseline has been obtained. The micro-ITT population will be used for efficacy analyses.

9.1.4 Per-protocol Population (PP)

All micro-ITT subjects who completed the study without any major protocol deviation.

9.2 Sample Size and Statement of Power

It is assumed that the proportion of subjects with Clinical Cure will be 65% in the placebo group, and 85% in the 20 mg/kg dose group. With 69 subjects per group, there will be > 90% power for a statistically significant difference at a two-sided 0.05 level of significance. Sample size calculation was performed based on Fisher's Exact test using binomial enumerations (PASS version 14). Assuming a 10% drop-out rate, 154 subjects (77 per group) will be randomized.

9.3 Statistical Methods

Continuous data will be summarized by means, standard deviations, median, min, and max. Categorical data will be summarized by frequency and percentages.

The primary endpoint of Clinical Cure rate at Day 21 will be analyzed using a stratified Cochran-Mantel-Haenszel (CMH) test. The CMH test will be stratified by baseline randomization strata. Time to Clinical Cure will be analyzed using a stratified log rank test. Other continuous endpoints will be analyzed using an Analysis of Covariance (ANCOVA), with treatment as a main effect, site, and baseline strata as covariates. Treatment by site interaction will be evaluated separately. Secondary endpoints will be analyzed using a sequential procedure in predefined order. Categorical variables will be analyzed using a stratified CMH test.

The primary comparisons for all endpoints will be between the 20 mg/kg dose group and placebo and will be done at 0.05 level of significance. The details of the planned analyses will be provided in the Statistical Analysis Plan.

9.3.1 Demographics, Baseline Characteristics, and Disposition

Demographics and baseline characteristics will be summarized by treatment group and overall. Disposition will be summarized by treatment group, and various outcomes (completed or discontinued the study, and reasons for discontinuations, etc.).

9.3.2 Safety analysis

Safety evaluations will include treatment emergent adverse events, vital signs, physical exam, and laboratory values. Safety will be summarized by treatment group. All treatment emergent adverse events, and serious adverse events, will be coded using the Medical Dictionary for Regulatory Activities (MedDRA). Relationship to treatment, as well as severity will also be summarized. Changes in vital signs and physical exam will be summarized by group. Changes in laboratory values, as well as shifts (normal-> abnormal) will be summarized by treatment group.

9.3.3 Pharmacokinetic analyses

Two types of pharmacokinetic analyses will be performed to assess the PK hypothesis that the PK profile of Aerucin® in the target patient population is similar to the profile observed in healthy human volunteers (HV). The first pharmacokinetic analysis will consist of a population PK (compartmental modeling) approach using the combined concentration data collected in the PK sub-study and the sparse concentration data, pooled with the available PK data from healthy volunteers (Study ARC-11-01). A compartmental population PK model will be developed and the effects of select intrinsic and extrinsic factors, including but not limited to patient status (e.g., HV versus patient with pneumonia), high or low bacterial load, and cause of admission [trauma or non-trauma]) on the PK of Aerucin® will be evaluated via covariate analysis. The population PK model will be described by the estimation of mean structural model parameters, the magnitude of IIV in these parameters, and the magnitude of RV.

The second pharmacokinetic analysis to be performed will be a non-compartmental analysis of the extensively sampled concentration-time data collected in the PK sub-study. The pharmacokinetic parameters to be derived from the individual concentration-time profiles will include: the maximum observed plasma concentration (C_{max}), the time of occurrence of C_{max} (t_{max}), the area under the plasma concentration-time curve from time 0 to Day 28 (AUC_{0-28}), the terminal elimination rate constant (λ_z), and, if data permits, the terminal half-life ($t_{1/2}$). Parameter estimates will be summarized and tabulated by individual and overall. Graphs of plasma concentration versus time profiles will be generated for each subject and graphs of mean \pm SD profiles will be generated to compare patient and HV data.

9.3.4 Interim Analysis

No interim analysis is planned.

9.3.5 Missing data

Assessing microbiological outcome at Day 7, 14, 21 (Primary Efficacy endpoint), and 28 will be done using the nearest microbiological data available prior to that day (last observation carried forward, LOCF).

Missing data for secondary efficacy endpoints will be analyzed using the LOCF approach.

For the purpose of sensitivity analysis, missing data will be imputed using baseline observation carried forward (BOCF) and observed case.

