4.3 Withdrawal Criteria

Participation of a subject in this clinical study may be discontinued, but not limited to, any of the following reasons:

- The subject withdraws consent or formally requests discontinuation from the study for any reason;
- The subject is lost to follow-up
- Improvement of pneumonia and discharge from ICU should NOT be considered withdrawal. All assessments including Clinical Cure assessment should be collected through Day 28

- Termination of the study by the Sponsor or the regulatory authority.

If a subject withdraws prematurely from the study due to the above criteria or any other reason, study staff should ensure that End of Study Visit data are recorded. The reason for subject withdrawal must be documented in the electronic case report form (eCRF).

In the case of subjects lost to follow-up, attempts to contact the subject must be made and documented in the subject's medical records, including whether the subject is alive at the time of contact.

Withdrawn subjects will not be replaced.

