
 1. To be performed if medically necessary. Follow-up airway specimens to be obtained as medically necessary and prior to extubation and at Day 28 (if not extubated prior to then) for quantitative or semi-quantitative culture. 2. SOFA and respiratory data to be collected on Day 0, 12 hours after treatment initiation and on Day 4, 7, 14, 21, 28 while intubated and mechanically ventilated. Parameters for SOFA score calculation should not be older than 72 hours. 3. ADA only at screening / baseline and Day 28, or at early termination. 4. Pre-dose PK sample to be obtained prior to treatment initiation. 5. PK samples to be obtained for the FULL PK sub-study at the following times after initiation of treatment: 2 hours (end of infusion), 4h, 12h, and 24 hours and 1 sample at each of the following visits: Day 4, 7, 14, 21, and 28. 6. PK samples for the SPARSE PK sub-study at the following times after initiation of treatment: 1 sample at 2 hours (end of infusion), 1 sample at either 4h, 12h, or 24 hours post-treatment initiation (inclusive) and 1 sample at any of the following visits: Day 4, 7, 14, 21, or 28. 7. Eligible subjects are randomized on Day -1, Treatment day is Day 0 for the purpose of monitoring and collecting the required samples over the first 24 hours. 8. Clinical Cure will be assessed at Day 7, 14, 21, 28 for the analytical purposes. 9. Discharge data to be obtained when discharge occurs or Day 28, whichever occurs first. 10. Patients with pneumonia who are intubated are eligible for screening regardless of the type of pneumonia, which will be recorded at the time of screening for all study subjects. 11. Vital signs will be recorded at baseline prior to treatment (time 0) and then at 1, 2, 4, 12, and 24 hours post treatment. Vital signs will also be recorded daily thereafter. 12. In addition to the screening timepoint, chest x-ray(s) are to be taken at any time as medically indicated. 13. Women of child bearing potential must take a urine or serum pregnancy test at the time of Screening. 14. For subjects with early discharge, effort must be made to perform all protocol defined procedures outlined for End of Study/Early Termination. 15. Subjects who decide to discontinue study assessments prior to Day 28 will receive a study exit safety follow-up phone call on key days (Day 4, 7, 14, 21, 28) until Day 28 (+7 days) to assess Clinical Cure, survival and the status of any adverse events. 16. Changes in PaO₂/FiO₂ ratio (e.g. by arterial blood gases), if available and whenever possible OR changes in non-invasive measures of oxygenation (e.g. by pulse oximetry) 17. A few days before or after the specified date is acceptable (± 2 days) 					

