#### **6.1.5. Handling of Dropouts and Missing Data**

Missing data will be handled as follows:

- For clinical outcome at Day 7, 14, 21, and 28, missing data will be handled using the nearest clinical data available prior to that day, i.e. last observation carried forward (LOCF) approach.
- For microbiological outcome at Day 7, 14, 21, and 28, missing data will be handled using the nearest microbiological data available prior to that day, i.e. **LOCF approach**.
- In cases of missing or incomplete dates [e.g. adverse event (AE) and concomitant medications], the missing component(s) will be assumed as the most conservative value possible. For example, AEs with missing start dates, but with stop dates either overlapping into the treatment period or missing, will be counted as treatment-emergent, taking the **worst-case approach**. When partial dates are present in the data, both a partial start date and/or a partial stop date will be evaluated to determine whether it can be conclusively established that the AE started prior to the start of study drug or ended prior to the start of study drug. If the above cannot be conclusively established based on the partial and/or present dates, then the AE will be considered as treatment-emergent. Actual data values will be presented in the data listings.
- A conservative approach will be taken to assess the relationship of an AE to study drug: if the relationship of an event is missing, it will be considered treatment-related. Missing severity for an AE will not be imputed.
- **Missing values for other variables will not be imputed** and only observed values will be used in data analyses and summaries.

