##### **6.4.2.2. Mortality**

All-cause mortality and pneumonia-related mortality rate by Day 7, 14, 21, and 28 will be tabulated by treatment group for the micro-ITT Population and analyzed using a stratified CMH test based on the stratification factors at randomization. The P-value from the stratified CMH test will be presented. In addition, plots of the Kaplan-Meier estimate of the survival distribution function over time will be presented by treatment group.

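### Day 28 mortality has no single rule for subjects whose vital status stays unknown: the protocol's LOCF scores them alive, while the SAP's natural reading leaves them out

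*Protocol*

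**What the plan says.** **Protocol.** Section 9.3.5 states: "Missing data for secondary efficacy endpoints will be analyzed using the LOCF approach". It makes no exception for mortality, which section 7.2 lists as secondary endpoints 3 (all-cause) and 4 (pneumonia-related). For sensitivity, "missing data will be imputed using baseline observation carried forward (BOCF) and observed case".

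**SAP, missing data.** Section 6.1.5 applies carry-forward to two named groups. The first reads "For clinical outcome at Day 7, 14, 21, and 28, missing data will be handled using the nearest clinical data available" before that day; the second is microbiological outcome on the same days. For everything else, "Missing values for other variables will not be imputed" and "only observed values will be used in data analyses and summaries". The section does not say where mortality belongs.

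**SAP, mortality.** Section 6.4.2.2 states: "All-cause mortality and pneumonia-related mortality rate by Day 7, 14, 21, and 28 will be tabulated by treatment group for the micro-ITT Population". The test is a stratified CMH test, and Kaplan-Meier curves are plotted in addition. The section gives no denominator, censoring rule or rule for unknown status. Other sections do supply such details: 6.4.1.1 gives a denominator rule for the primary analysis, and 6.4.2.1 a censoring rule for time to cure.

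**Collection.** Footnote 15 of Table 6-1 and protocol section 8.8 provide calls that assess survival, up to Day 28 (+7 days), for subjects who choose to stop assessments. For subjects lost to follow-up, section 4.3 requires documented contact attempts, "including whether the subject is alive at the time of contact", with no reference to Day 28.

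**The concern.** Mortality carries the survival hypothesis in protocol section 1.4. All-cause mortality at Day 28 is third in the SAP's fixed testing order (section 6.4.2), so its result affects which later endpoints can be claimed.

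Death differs from most endpoints under LOCF. The last observation of anyone who leaves alive is always alive, so carrying it forward can miss deaths but never add them. Leaving such subjects out instead assumes that they resemble those who stayed. If the protocol points to one rule and the SAP to the other, the same data can give different rates and p-values.

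**Working it through.** **Inputs.** Neither document states a mortality rate or an expected share with unknown vital status. The nearest figure is the 10% drop-out in protocol section 9.2. It reproduces as 69 / 0.9 = 76.7, rounded to 77 per group and 154 in total. It was set for the Clinical Cure sample size, so it serves here only as a probable upper bound on unknown status. All other values are assumptions:

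- M = true Day 28 mortality, 30% (range 20% to 40%)
- d = share leaving alive with status never learned, 10% (range 5% to 10%)
- q = risk of death by Day 28 among those leavers, 0 to 2M

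**Formulas.** Recorded deaths, as a share of all subjects, are M - dq.

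- LOCF rate = M - dq
- Observed-only rate = (M - dq) / (1 - d)
- Recorded deaths over all micro-ITT subjects = M - dq, the same as LOCF

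**Level of the rate, M = 30%, d = 10%.**

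| q | LOCF | Observed-only | Gap (points) |
|---|---|---|---|
| 0% | 30.0% | 33.3% | 3.3 |
| 15% | 28.5% | 31.7% | 3.2 |
| 30% | 27.0% | 30.0% | 3.0 |
| 60% | 24.0% | 26.7% | 2.7 |

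LOCF is exact only at q = 0. Observed-only is exact at q = M, too high below that and too low above it. Over the full ranges, the LOCF error runs from 0 to -8 points and the observed-only error from -4.4 to +4.4.

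**The protocol's sensitivity analyses.** Everyone is alive at baseline, so BOCF gives the same mortality result as LOCF. That leaves observed case, which is the SAP's apparent main rule. The SAP's own sensitivity analyses cover the primary endpoint only.

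**Treatment difference, equal true mortality of 30%.** With the same d and q in both arms, neither rule creates a difference. With d = 5% in one arm and 15% in the other:

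- q = 60%, LOCF: (0.30 - 0.03) - (0.30 - 0.09) = 27.0% - 21.0% = 6.0 points
- q = 60%, observed-only: 0.27/0.95 - 0.21/0.85 = 28.4% - 24.7% = 3.7 points
- q = 0, LOCF: 0 points
- q = 0, observed-only: 0.30/0.95 - 0.30/0.85 = 31.6% - 35.3% = -3.7 points

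At 77 per arm, the two q = 60% differences give unstratified p = 0.38 and 0.62.

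**Effect on a test.** Take constructed counts of 23/77 deaths on placebo and 13/77 on active. The unstratified chi-square p-value is 0.057 under LOCF. Observed-only gives 0.053 with 8 and 8 leavers (placebo, active), 0.124 with 4 and 12, and 0.019 with 12 and 4.

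**Does censoring cure it?** Keep d = 5% and 15% and q = 60%. Let all exits fall on Day 10 and spread recorded deaths evenly over 28 days. Kaplan-Meier survival at Day 28 is:

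- 5% arm: deaths by Day 10 = 0.27 × 10/28 = 0.0964; later deaths = 0.1736. Survival = 0.9036 × (1 - 0.1736/0.8536) = 0.720, so mortality is 28.0%.
- 15% arm: deaths by Day 10 = 0.075; later deaths = 0.135. Survival = 0.925 × (1 - 0.135/0.775) = 0.764, so mortality is 23.6%.

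The false difference is 4.4 points, against 3.7 for observed-only. Censoring alone does not remove bias from informative withdrawal.

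**The case against.** **The data are largely collected.** Subjects who stop assessments are called about survival at Day 28 or up to 7 days later, and a completed call in that forward window settles Day 28 status. Section 4.3 says that discharge after improvement is not withdrawal, and section 8.8 adds calls for cured, discharged subjects who cannot attend. Section 8.5 requires SAEs, which include deaths, to be reported until 28 days after dosing. Section 6.7 counts death as a possible reason for early termination, so some early exits have known status. This stands and narrows the affected group. It does not empty it: the calls are written for people who choose to stop assessments, and SAE reporting depends on the investigator learning of the death.

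A reader might infer from footnote 17 of Table 6-1, which allows the final visit two days early, that completers are scored alive at Day 28 without being observed. SAE reporting covers deaths in those days, so this adds little.

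**The conflict is inferred.** A reader might see an outright contradiction. The documents do not support that, because neither missing-data rule names mortality. Clinical outcome in SAP 6.1.5 could be stretched to cover it, since mortality is tabulated on the same four days, although SAP section 6.4.1.1 uses the term for the cure/failure assessment. Dividing recorded deaths by all micro-ITT subjects would match the protocol's LOCF. Protocol section 9.3 also leaves details to the SAP. All of this is fair, but the SAP neither flags a departure from the protocol nor classifies mortality, so several programs remain defensible.

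**The inputs are extreme.** The 5% and 15% exits and the 60% later mortality have no source in the documents, and the differences they produce are far from significance. This stands.

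**Conclusion.** The point holds as a gap in the specification of a tested endpoint. The protocol's stated rule understates mortality unless no leaver dies. The SAP's natural reading is a different rule, and its mortality section does not settle the denominator or unknown status. Only subjects whose status stays unknown are affected, mainly those lost to follow-up or refusing contact.

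The size cannot be fixed from the documents. At an assumed 30% mortality and 10% unknown, the two rules differ by about 3 points at any given leaver risk. When true mortality is equal, a false treatment difference appears only if exit shares or leaver risk differ by arm.

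Two stronger readings are not supported. One is that both rules are always biased; observed-only is unbiased when leavers have average risk. The other is that the choice of document will decide whether the testing chain continues. Constructed counts with 12 and 4 leavers do cross 0.05, but nothing in the documents makes that imbalance likely, and step 3 is reached only if the cure endpoints ahead of it succeed.

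**What to change.** 1. **Protocol 4.3.** Extend the existing Day 28 (+7 days) vital-status check to withdrawn and lost subjects, through hospital records or contact as consent and local law allow. Record the date of death or the date last known alive.
2. **Protocol 9.3.5, SAP 6.1.5 and SAP 6.4.2.2.** State that LOCF and BOCF do not apply to mortality, and give one rule for unknown Day 28 status. Keep the Day 28 proportion as the endpoint and estimate it by Kaplan-Meier, censoring at the date last known alive, in line with the curves that the SAP already plots. For pneumonia-related mortality, count other deaths as competing events.
3. **Sensitivity.** Add a best/worst-case or tipping-point analysis, because censoring may be informative.

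Replacing the CMH test with a log-rank test is not required. If CMH stays, one sentence should say how subjects with unknown status enter its table.

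The cost is wording in both documents, a few extra chart checks or calls, and one added sensitivity table.
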